Time between inclusion and the 1st change in dose (days) - incident patients	N Missing data Mean (SD) Median [Min; Max] [Q1; Q3]	XX XX XX.XX (X.XX) XX.X [XX.X; XX.X] [XX.X; XX.X]
Time between inclusion and the 1st change in dose (days) - prevalent patients	N Missing data Mean (SD) Median [Min; Max] [Q1; Q3]	XX XX XX.XX (X.XX) XX.X [XX.X; XX.X] [XX.X; XX.X]
Mean time between 2 changes in dose (days)	N Missing data Mean (SD) Median [Min; Max] [Q1; Q3]	XX XX XX.XX (X.XX) XX.X [XX.X; XX.X] [XX.X; XX.X]
Mean time between 2 changes in dose (days) – incident patients	N Missing data Mean (SD) Median [Min; Max] [Q1; Q3]	XX XX.XX (X.XX) XX.X [XX.X; XX.X] [XX.X; XX.X]
Mean time between 2 changes in dose (days) – prevalent patients	N Missing data Mean (SD) Median [Min; Max] [Q1; Q3]	XX XX.XX (X.XX) XX.X [XX.X; XX.X] [XX.X; XX.X]

^{*} The same patient may be counted several times if several changes/increases/reductions took place.

Programmer note:

- Time between inclusion and the 1st change in dose = date of 1st change in dose inclusion date.
- Mean time between change in dose = mean of times between two different consecutive doses per patient (after inclusion).

Using the same template:

Table 14.2.2.2.5: Changes in the Dose of Treatment Started or Ongoing at Inclusion During the Study: Everolimus – Reference Set

Programmer note: for the variables "Reasons for dose reduction during the study" and "Reasons for dose increase during the study", the modalities are "Adverse event related to everolimus," "Adverse event not related to everolimus," "Adverse event (relationship with everolimus not stated)", "Patient's choice" and "Doctor's choice".

Table 14.2.2.2.6: Changes in the Dose of Treatment Started or Ongoing at Inclusion During the Study: Interferon Alpha– Reference Set

Programmer note: do not show changes in dose by increase and decrease.

Table 14.2.2.7: Changes in the Dose of Treatment Started or Ongoing at Inclusion During the Study: Chemotherapy – Reference Set

		Chemotherapy (N=XX)
Change in dose step during the study	N	XX
889	Missing data	XX
	0	XX (XX.X%)
	1	XX (XX.X%)
		XX (XX.X%)
Type of change in dose step during the study*	N	XX
-, FrBB	Missing data	XX
	Increase	XX (XX.X%)
	Decrease	XX (XX.X%)
	•••	XX (XX.X%)
At least one dose reduction during the study	N	XX
	Missing data	XX
	Yes	XX (XX.X%)
	No	XX (XX.X%)
At least one dose increase during the study	N	XX
	Missing data	XX
	Yes	XX (XX.X%)
	No	XX (XX.X%)
Reasons for dose reduction during the study*	N	XX
a ,	Missing data	XX
	Adverse event	XX (XX.X%)

Table 14.2.2.7: Changes in the Dose of Treatment Started or Ongoing at Inclusion During the Study: Chemotherapy – Reference Set

		Chemotherapy (N=XX)
	Patient's choice	XX (XX.X%)
	Doctor's choice	XX (XX.X%)
	Other	XX (XX.X%)
Reasons for dose increase during the study	N	XX
	Missing data	XX
	Adverse event	XX (XX.X%)
	Patient's choice	XX (XX.X%)
	Doctor's choice	XX (XX.X%)
	Other	XX (XX.X%)
Fime between inclusion and the 1st change in dose (days)	N	XX
	Missing data	XX
	Mean (SD)	XX.XX (X.XX)
	Median	XX.X
	[Min; Max]	[XX.X; XX.X]
	[Q1; Q3]	[XX.X; XX.X]
Time between inclusion and the 1st change in dose (days)-incident patients	N	XX
	Missing data	XX
	Mean (SD)	XX.XX (X.XX)
	Median	XX.X
	[Min; Max]	[XX.X; XX.X]
	[Q1; Q3]	[XX.X; XX.X]
Time between inclusion and the 1st change in dose (days) -prevalent patients	N	XX
	Missing data	XX
	Mean (SD)	XX.XX (X.XX)
	Median	XX.X
	[Min; Max]	[XX.X; XX.X]
	[Q1; Q3]	[XX.X; XX.X]
Mean time between change in dose (days)	N	XX
	Missing data	XX
	Mean (SD)	XX.XX (X.XX)
	Median	XX.X
	[Min; Max]	[XX.X; XX.X]
	[Q1; Q3]	[XX.X; XX.X]
Mean time between change in dose (days) – incident patients	N	XX
	Missing data	XX
	Mean (SD)	XX.XX (X.XX)
	Median	XX.X
	[Min; Max]	[XX.X; XX.X]
	[Q1; Q3]	[XX.X; XX.X]
Mean time between change in dose (days) – prevalent patients	N	XX
	Missing data	XX
	Mean (SD)	XX.XX (X.XX)
	Median	XX.X
	[Min; Max] [Q1; Q3]	[XX.X; XX.X] [XX.X; XX.X]

^{*} The same patient may be counted several times if several changes/increases/reductions took place.

Programmer note:

• Time between inclusion and the 1st change in dose = date of 1st dose modification – date of inclusion.

• Mean time between change in dose = mean of times between two different consecutive doses (after inclusion).

Using the same template:

Table 14.2.2.2.8: Changes in the Dose of Treatment Started or Ongoing at Inclusion During the Study: Somatostatin Analog – Reference Set

Programmer note: do not show changes in dose by increase and decrease.

Table 14.2.2.2.9: Number of Courses During the Study of Metabolic Radiotherapy Initiated or Ongoing at Inclusion – Reference Set

		Metabolic radiotherapy (N=XX)
Number of courses since initiation	N	XX
	Missing data	XX
	Mean (SD)	XX.XX (X.XX)
	Median	XX.X
	[Min; Max]	[XX.X; XX.X]
	[Q1; Q3]	[XX.X; XX.X]
Number of courses since initiation (N(%))	N	XX
	Missing data	XX
	1	XX (XX.X%)
	2	XX (XX.X%)
		XX (XX.X%)
Number of courses during the study*	N	XX
	Missing data	XX
	Mean (SD)	XX.XX (X.XX)
	Mean	XX.X
	[Min; Max]	[XX.X; XX.X]
	[Q1; Q3]	[XX.X; XX.X]
Number of courses during the study (N(%))	N	XX
	Missing data	XX
	1	XX (XX.X%)
	2	XX (XX.X%)
		XX (XX.X%)

^{*} only post-inclusion courses are shown.

Table 14.2.2.2.10: Lines of Treatment Received During the Study – Reference Set

		Targeted therapies (N=XX)	Other treatments (N=XX)	Total (N=XX)
Number of live of American description of American description				
Number of lines of treatment received during the study	N	XX	XX	XX
,	Missing data	XX	XX	XX
	Mean (SD)	XX.XX (X.XX)	XX.XX (X.XX)	XX.XX (X.XX)
	Median [Min; Max] [Q1; Q3]	XX.X [XX.X; XX.X] [XX.X; XX.X]	XX.X [XX.X; XX.X] [XX.X; XX.X]	XX.X [XX.X; XX.X] [XX.X; XX.X]
Number of lines of treatment received during the study $(N(\%))$	N	XX	XX	XX
study (14(70))	Missing data 1 2	XX XX (XX.X%) XX (XX.X%)	XX XX (XX.X%) XX (XX.X%)	XX XX (XX.X%) XX (XX.X%)
Type of lines of treatment received during the study (other than those being received at inclusion)	N	XX	XX	XX
()	Missing data Line 1 Line 2	XX XX (XX.X%) XX (XX.X%)	XX XX (XX.X%) XX (XX.X%)	XX XX (XX.X%) XX (XX.X%)
Total number of lines of treatment received*	 N Missing data	XX XX	XX XX	XX XX
	Mean (SD)	XX.XX (X.XX)	XX.XX (X.XX)	XX.XX (X.XX)
	Median [Min; Max] [Q1; Q3]	XX.X [XX.X; XX.X] [XX.X; XX.X]	XX.X [XX.X; XX.X] [XX.X; XX.X]	XX.X [XX.X; XX.X] [XX.X; XX.X]
Total number of lines of treatment received* (N(%))	N Missing data 1 2	XX XX XX (XX.X%) XX (XX.X%)	XX XX XX (XX.X%) XX (XX.X%)	XX XX XX (XX.X%) XX (XX.X%)

^{*} Previous lines and lines received during the study.

Note: The lines of treatment will need to be reviewed prior to the analysis (data review) in order to identify these as such in planning the analyses.

Using the same template:

Table 14.2.2.2.11: Main Concomitant Treatment Lines Received During the Study – Reference Set

Listing 14.2.2.2.1: Treatment Regimen (Previous Lines of Treatment and Administered During the Study) – Reference Set

Patient Sex Age	Reference set	Group		Type of treatment	main	No. of the main concomitan t treatment line		Concomitan t treatment			Reason for discontinuatio n
XXXX X XXXX X XX	Yes/No	XXX	Xxxx	- XXXX	- XXXX	- XXXX	- XXXX	- XXXX	- xxxx	- XXXX	- XXXX

Programmer note:

Table 14.2.2.2.12: Treatments Received at Least Once During the Study According to the Treatment at Inclusion – Reference Set

	Targeted therapies (N=XX)	Other treatments (N=XX)	Total (N=XX)
Number of patient receiving a main treatment at least once during the study $(N(\%))$:	XX (XX.X%)	XX (XX.X%)	XX (XX.X%)
- Targeted therapy - Everolimus	XX (XX.X%) XX (XX.X%)	XX (XX.X%) XX (XX.X%)	XX (XX.X%) XX (XX.X%)
- Sunitinib	XX (XX.X%)	XX (XX.X%)	XX (XX.X%)
- Other treatment	XX (XX.X%)	XX (XX.X%)	XX (XX.X%)
- Chemotherapy	XX (XX.X%)	XX (XX.X%)	XX (XX.X%)
- Somatostatin analog	XX (XX.X%)	XX (XX.X%)	XX (XX.X%)
- Metabolic radiotherapy	XX (XX.X%)	XX (XX.X%)	XX (XX.X%)
- Interferon alpha	XX (XX.X%)	XX (XX.X%)	XX (XX.X%)
- Other	XX (XX.X%)	XX (XX.X%)	XX (XX.X%)
Number of patients receiving at least one main treatment and/or a combination during the study (N(%)):	XX (XX.X%)	XX (XX.X%)	XX (XX.X%)
- Targeted therapy	XX (XX.X%)	XX (XX.X%)	XX (XX.X%)
- Everolimus	XX (XX.X%)	XX (XX.X%)	XX (XX.X%)
- Sunitinib	XX (XX.X%)	XX (XX.X%)	XX (XX.X%)
- Other treatment	XX (XX.X%)	XX (XX.X%)	XX (XX.X%)

^{*} In the case of previous treatment, the length of the targeted therapies is to be taken directly from the e-CRF (data not calculated).

Table 14.2.2.2.12: Treatments Received at Least Once During the Study According to the Treatment at Inclusion – Reference Set

	Targeted therapies (N=XX)	Other treatments (N=XX)	Total (N=XX)
- Chemotherapy	XX (XX.X%)	XX (XX.X%)	XX (XX.X%)
- Somatostatin analog	XX (XX.X%)	XX (XX.X%)	XX (XX.X%)
- Metabolic radiotherapy	XX (XX.X%)	XX (XX.X%)	XX (XX.X%)
- Interferon alpha	XX (XX.X%)	XX (XX.X%)	XX (XX.X%)
- Other	XX (XX.X%)	XX (XX.X%)	XX (XX.X%)
Number of patients receiving at least once during the study:			
Treatment XX alone	XX (XX.X%)	XX (XX.X%)	XX (XX.X%)
Combination 1	XX (XX.X%)	XX (XX.X%)	XX (XX.X%)
Combination 2	XX (XX.X%)	XX (XX.X%)	XX (XX.X%)

Using the same template:

Table 14.2.2.2.13: Treatments Received at Least Once During the Study According to Treatment at Inclusion – Safety Analysis Set

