The patients will be followed up prospectively throughout the period of the study (24-month follow-up) from their inclusion into the study. The follow-up visits will be conducted during usual patient tumour assessment consultations at the centres (ie, approximately every 2 to 3 months) independently of interruptions, changes or discontinuations of treatment which may have occurred. No consultations will be imposed by the protocol for this observational study and the follow-up and treatment details will remain according to the judgment of the doctor.

The general plan of the study is shown in the figure below.

Figure 1. *General plan of the study*

The study will include a retrospective and/or prospective data collection period, depending on whether the patient is prevalent or incident in terms of his/her tumour treatment at the time of his/her inclusion into the study as described in the table below.

Tableau 1: Collection of Retrospective and/or Prospective Data

	'Prevalent' patients	'Incident' patients
Retrospective	- Initial diagnosis of the tumour	- Initial diagnosis of the
collection	- Previous cancer treatments	tumour
	- Patient characteristics and description of the	- Previous cancer
	disease when the study treatment was started	treatments
	- Initiation of the study treatment and	
	reference data on starting this treatment	
	- Safety (see paragraph 7 of the	
	Pharmacovigilance protocol):	
	- If the treatment is ongoing at inclusion and	
	involves everolimus, retrospective record of	
	adverse events:	
	- Clearly linked to everolimus since it	
	was started until inclusion.	
	- Clearly linked to a Pfizer product	
	since first line management of the	
	disease and until the inclusion.	

	 For all other treatments ongoing at inclusion (Sunitinib, chemotherapy, somatostatin analogs, metabolic radiotherapy or interferon alpha), retrospective collection of adverse events: Clearly linked to a Pfizer product since the first line of management of the disease until inclusion. 	

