5.6. Analysis of Secondary Objectives

The analysis of patient characteristics is shown in Section 5.4.1.

The following analysis will also be carried out in order to meet the secondary objectives of the study:

• Patient management: frequency of visits, tumour assessment methods, therapeutic management.

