9.3. Analysis of the Secondary Objectives

9.3.1. Management of Patients

Table 14.2.2.2.1: Number and Frequency of Tumour Assessment Visits – Reference Set

		Targeted therapies (N=XX)	Other treatments (N=XX)	Total (N=XX)
N1	N	VV (VV V0/)	VV (VV V0/)	VV (VV V0/)
Number of tumour assessments		XX (XX.X%) XX	XX (XX.X%) XX	XX (XX.X%) XX
	Missing data			
	Mean (SD)	XX.XX (X.XX)	XX.XX (X.XX)	XX.XX (X.XX)
	Median	XX.X	XX.X	XX.X
	[Min; Max]	[XX.X; XX.X]	[XX.X; XX.X]	[XX.X; XX.X]
	[Q1; Q3]	[XX.X; XX.X]	[XX.X; XX.X]	[XX.X; XX.X]
Number of tumour assessments (N(%))	N	XX	XX	XX
	Missing data	XX	XX	XX
	0	XX (XX.X%)	XX (XX.X%)	XX (XX.X%)
	1	XX (XX.X%)	XX (XX.X%)	XX (XX.X%)
	2	XX (XX.X%)	XX (XX.X%)	XX (XX.X%)
	-	()	((,
Frequency of investigations (1)	N	XX	XX	XX
rrequency of investigations (1)	Missing data	XX	XX	XX
	X/year	XX (XX.X%)	XX (XX.X%)	XX (XX.X%)
	•	XX (XX.X%)	XX (XX.X%)	XX (XX.X%)
	•••	$\Lambda\Lambda$ $(\Lambda\Lambda.\Lambda/0)$	$\Lambda\Lambda$ ($\Lambda\Lambda.\Lambda/0$)	$\Lambda\Lambda$ $(\Lambda\Lambda.\Lambda/0)$
Time between investigations (months)	N	XX	XX	XX
	Missing data	XX	XX	XX
	Mean (SD)	XX.XX (X.XX)	XX.XX (X.XX)	XX.XX (X.XX)
	Median	XX.X	XX.X	XX.X
	[Min; Max]	[XX.X; XX.X]	[XX.X; XX.X]	[XX.X; XX.X]
	[Q1; Q3]	[XX.X; XX.X]	[XX.X; XX.X]	[XX.X; XX.X]
Time between investigations (1) (N(%))	N	XX	XX	XX
Time octween investigations (1) (14(70))	Missing data	XX	XX	XX
	<4 months	XX (XX.X%)	XX (XX.X%)	XX (XX.X%)
	>4 months	XX (XX.X%)	XX (XX.X%)	XX (XX.X%)
	1 of 1 '1	***** (**** **** **		
	1 st decile	XX (XX.X%)	XX (XX.X%)	XX (XX.X%)
	2 nd decile	XX (XX.X%)	XX (XX.X%)	XX (XX.X%)
		XX (XX.X%)	XX (XX.X%)	XX (XX.X%)

⁽¹⁾ calculated as a proportion of the total number of investigations performed and not the number of patients.

Programmer note: for the variables "Time between investigations", N=number of times between investigations. The inclusion visits are not counted as a tumour assessment but are retained in the calculation of times between investigations in order to obtain the first time between the inclusion visit and the first tumour assessment.

Frequency of investigations = number of investigations / ((date of last visit–date of inclusion)/365.25).

Table 14.2.2.2.2: Investigations Used for the Tumour Assessment – Reference Set

		Targeted therapies (N=XX)	Other treatments (N=XX)	Total (N=XX)
CT Scan – performed at least once during the study regardless	N	XX	XX	XX
of treatment received	Missing data	XX	XX	XX
	Yes	XX (XX.X%)	XX (XX.X%)	XX

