Programmer note: the number of uses of an investigation should be analysed in the population of patients with at least one investigation (this applies for all investigations).

Frequency of investigations = number of investigations (by type or all)/((study end date-inclusion date)/365.25).

Time between 2 imaging investigations per patient = date of the second imaging assessment – date of the 1st imaging investigation in the same patient.

Table 14.2.2.2: Changes to Treatment Documented in the Study – Reference Set

		Targeted therapies (N=XX)	Other treatments (N=XX)	Total (N=XX)
Change in ongoing treatment at inclusion	N	XX	XX	XX
	Missing data	XX	XX	XX
	Yes	XX (XX.X%)	XX (XX.X%)	XX (XX.X%)
	No	XX (XX.X%)	XX (XX.X%)	XX (XX.X%)
At least one change in concomitant treatment	N	XX	XX	XX
	Missing data	XX	XX	XX
	Yes	XX (XX.X%)	XX (XX.X%)	XX (XX.X%)
	No	XX (XX.X%)	XX (XX.X%)	XX (XX.X%)

Table 14.2.2.2.4: Changes in the Dose of Treatment Started or Ongoing at Inclusion During the Study: Sunitinib – Reference Set

		Sunitinib (N=XX)
Change in dose step during the study	N	XX
	Missing data	XX
	0	XX (XX.X%)
	1	XX (XX.X%)
	•••	XX (XX.X%)
Type of change in dose step during the study*	N	XX
	Missing data	XX
	Increase	XX (XX.X%)
	Reduction	XX (XX.X%)
		XX (XX.X%)
Dose after increase $(N(\%))^*$	N	XX
	Missing data	XX
	37.5 mg/day	XX (XX.X%)
	25 mg/day	XX (XX.X%)
	•••	XX (XX.X%)
Dose after reduction $(N(\%))^*$	N	XX
	Missing data	XX
	37.5 mg/day	XX (XX.X%)
	25 mg/day	XX (XX.X%)
		XX (XX.X%)
At least one dose reduction during the study	N	XX
Z ,	Missing data	XX
	Yes	XX (XX.X%)
	Non	XX (XX.X%)
At least one dose increase during the study	N	XX
z ,	Missing data	XX
	Yes	XX (XX.X%)
	Non	XX (XX.X%)
Reasons for dose reduction during the study	N	XX

Table 14.2.2.2.4: Changes in the Dose of Treatment Started or Ongoing at Inclusion During the Study: Sunitinib – Reference Set

		Sunitinib (N=XX)
	Missing data Adverse event Patient's choice Doctor's choice Other	XX XX (XX.X%) XX (XX.X%) XX (XX.X%) XX (XX.X%)
Reasons for dose increase during the study*	N Missing data Adverse event Patient's choice Doctor's choice Other	XX XX XX (XX.X%) XX (XX.X%) XX (XX.X%) XX (XX.X%)
Time between inclusion and the 1 st change in dose (days)	N Missing data Mean (SD) Median [Min; Max] [Q1; Q3]	XX XX XX.XX (X.XX) XX.X [XX.X; XX.X] [XX.X; XX.X]

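### SAP Table 14.2.2.2.1 divides the classes of a per-patient yearly frequency by the number of investigations, so the row does not describe patients

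*SAP*

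**What the plan says.** SAP section 5.6 lists among the secondary analyses "Patient management: frequency of visits, tumour assessment methods, therapeutic management". Section 9.3.1 delivers part of this in Table 14.2.2.2.1, by treatment group and in total.

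Two rows of that table carry footnote (1): the yearly frequency, laid out as X/year classes with n (%), and the classed time between investigations. The footnote says their percentages are "calculated as a proportion of the total number of investigations performed and not the number of patients".

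The programmer note under the table reads "Frequency of investigations = number of investigations / ((date of last visit–date of inclusion)/365.25", with the closing bracket following. It sets a unit of count only for the time-between rows, where N is the number of intervals. It sets none for the frequency row.

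The rows giving the number of assessments per patient, with classes starting at 0, do not carry the footnote. Neither do the X/year rows of Table 14.2.2.2.2, which give yearly frequency by imaging type.

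**The concern.** Each patient has one assessment count, one follow-up time and therefore one frequency. A table of frequency classes should say what share of patients falls in each class. The footnote expressly rules patients out as the base and puts investigations in their place. The SAP does not say what is then counted in the numerator, and neither possible choice gives a distribution of patients.

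The row has some use beyond its own table. SAP section 6.2 says progression-free survival will be less precise than in a clinical trial because real-world assessment intervals are longer. A reader wanting to know how closely patients were assessed would look here.

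**Working it through.** The table is an empty shell, so the plan gives no figure to reproduce. The check compares the share of patients in each class with what the footnote would produce.

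**Inputs from the documents**
- Percentage base: total investigations (footnote 1, Table 14.2.2.2.1).
- Frequency: "number of investigations / ((date of last visit–date of inclusion)/365.25" (programmer note, same table).
- Expected visit interval: "approximately every 2 to 3 months" (SAP 3.3), that is 12/3 = 4 to 12/2 = 6 per year.
- Planned follow-up: 24 months (SAP 3.3). Planned patients: 150 (SAP 4.2).

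**Assumptions.** The splits between rates and the follow-up patterns below are illustrative. The documents give neither.

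**Reading 1: each patient counted once, divided by all investigations.** The classes add to P/I, with P patients and I investigations. For 150 patients with 8 each, 150/1200 = 12.5%. For 75 at 4/year and 75 at 6/year over 24 months, I = 75×4×2 + 75×6×2 = 1500, so each class shows 75/1500 = 5% and the total is 10%.

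**Reading 2: investigations from patients in the class, divided by all investigations.** Patient i has weight n_i = r_i × t_i (rate times years), and the class share is the sum of n_i in the class over the sum of all n_i.

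| Scenario (75 patients at 4/year, 75 at 6/year) | Investigations, 4/year + 6/year | 6/year class shown | Patients at 6/year |
|---|---|---|---|
| All followed 24 months | 600 + 900 = 1500 | 900/1500 = 60% | 50% |
| 4/year followed 12 months, 6/year 24 months | 300 + 900 = 1200 | 900/1200 = 75% | 50% |
| All stop at 8 visits | 600 + 600 = 1200 | 600/1200 = 50% | 50% |
| 6/year leave at 12 months, 4/year stay 24 | 600 + 450 = 1050 | 450/1050 = 42.9% | 50% |

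The mean rate implied by these weights is mean(r) + Cov(n, r)/mean(n), so the direction follows the sign of the covariance between count and rate. In the first row n is 8 or 12 and r is 4 or 6: Cov = (32 + 72)/2 − 10×5 = 2, and 5 + 2/10 = 5.20. In the last row n is 8 or 6: Cov = (32 + 36)/2 − 7×5 = −1, and 5 − 1/7 = 4.86.

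A simulation with log-normal rates and follow-up capped at 2 years (per-patient mean about 5.05) gave weighted means of 5.56, 5.38, 5.15 and 5.01. The correlations between rate and follow-up, on the underlying normal scale, were +0.5, 0, −0.5 and −0.8.

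**Patients with no assessment.** Take 15 at 0/year, 68 at 4/year and 67 at 6/year, the last two groups followed 24 months. Investigations are 0 + 544 + 804 = 1348. The 0/year class is 15/150 = 10% of patients but shows 0%. The 6/year class is 67/150 = 44.7% of patients but shows 804/1348 = 59.6%.

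**The other row with the footnote.** For time between investigations the unit is the interval. The note keeps the inclusion visit as the start of the first interval, so a patient with k assessments supplies k intervals, and the two totals agree apart from missing dates.

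**The case against.** Four points can be made for leaving the table alone.

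- **Patient-level information is planned elsewhere.** The same table gives assessments per patient, and Table 14.2.2.2.2 gives yearly rates by imaging type with means, medians and classes. This stands in part. The counts are not adjusted for follow-up. The note to Table 14.2.2.2.2 uses a different end date, "Frequency of investigations = number of investigations (by type or all)/((study end date-inclusion date)/365.25", and although it mentions all investigations, the shell has rows only for single modalities and for CT or MRI combined. The rate for all assessments up to the last visit appears only in the faulty row.
- **The size depends on the scenario.** This stands. SAP 5.5.1 says eight visits are possible in the eCRF, with a further one if the eighth falls before 24 months. If every patient stopped at eight visits, Reading 2 would show no shift. Reading 1 would still fail to reach 100%.
- **The row is descriptive, without a test.** This stands, and SAP 6.4 already says comparison of treatment effects between the groups is not strictly appropriate. A reader might infer that the footnote spoils a treatment comparison. It could create an apparent difference in assessment frequency where follow-up differs, but no planned inference rests on this row.
- **Interval-level percentages are legitimate.** This stands for the time-between row. A reader might extend the criticism to its classes of under and over 4 months, but the note sets intervals as the unit there, and the percentages are coherent on that base.

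**Conclusion.** Wrong as written, with limited impact. A value defined once per patient is given a base that excludes patients, and no reading of the footnote yields the distribution of patients. With 150 patients at 4 or 6 per year in equal halves, the 6-per-year class would show 60% under equal 24-month follow-up and 42.9% if those patients left at 12 months, against a true 50%. If each patient is counted once, the classes in those two cases total 10% (150/1500) and 14.3% (150/1050).

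A reader might infer that the footnote makes follow-up look more intensive than it was. That holds when follow-up is equal, or unrelated to the assessment rate. It does not hold if visit counts are capped, and it reverses if often-assessed patients leave early. The documents do not show which pattern applies, so the supported statement is distortion in either direction.

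The figures rest on the assumed rates and follow-up times. The mismatch of unit and base does not.

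**What to change.** - Remove footnote (1) from the frequency row of Table 14.2.2.2.1.
- State that N for this row is the number of patients with a calculable frequency, that is with follow-up time from inclusion to last visit, including those at 0 per year. Restricting N to patients with at least one assessment would drop a class the table itself expects and raise the apparent frequency: in the zero-assessment example, 67/135 = 49.6% at 6/year instead of 44.7%.
- Keep an event-level base on the classed time-between-investigations row only, and word it as the number of intervals to match the programmer note.
- While editing, align or justify the two end dates (last visit in Table 14.2.2.2.1, study end in Table 14.2.2.2.2).

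The cost is a footnote, a line in the programmer note and one denominator in the program. Nothing further has to be collected, and no primary result changes.
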